5.5.2 Methods of sample collection

5.5.2.1 Sampling of whole blood and plasma

Whole blood and plasma will be collected at time points shown in the [Flow Chart](#):

- to determine [¹⁴C]-radioactivity concentrations in whole blood and plasma
- to determine concentrations of BI 730357

Proprietary confidential information © 2018 Boehringer Ingelheim International GmbH or one or more of its affiliated companies

5.5.2.2 Sampling of whole blood and plasma for [¹⁴C]-radioactivity analysis in whole blood and plasma and quantification of BI 730357 in plasma

At each time point listed in the [Flow Chart](#), 4 mL (for time points from 1 h up to 72 h post-dose (inclusive)), or 8 mL (for the pre-dose, at time point 0.5 h and from time point 120 h up to 312 h post-dose) or 6 mL (for time points at ambulatory visits) blood will be taken from a forearm vein using a commercial vacutainer or monovette collection tube with K2-EDTA as anticoagulant. Withdrawal of blood will be done via an indwelling cannula or direct venae puncture.

It is planned that aliquots of all time points are prepared for determination of [¹⁴C]-radioactivity in whole blood and plasma.

Aliquots for bioanalysis of BI 730357 in plasma are planned to be prepared for up to 312 h after drug administration.

Premature stopping of blood sampling from 168 h onwards

In case [¹⁴C]-radioactivity in plasma samples is not detectable (<LLOQ 10 dpm/mL) at two consecutive time points for a subject, blood sampling can be stopped for this subject. However, all samples until and including the 168 h sample have to be taken.

For detailed description of blood sampling, sample handling, sample preparation, sample storage, tube labelling and sample shipment refer to the laboratory manual.

5.5.2.3 Sampling of plasma for metabolic profiling

At each time point listed in the [Flow Chart](#) for metabolic profiling sampling, blood will be withdrawn from a forearm vein using a commercial vacutainer or monovette collection tube with K2-EDTA as anticoagulant. Pre-dose 8 mL of blood will be taken and at all time points post-dose the maximum possible volume of blood will be drawn according to what is allowed considering the blood samples taken for all other samples except metabolic profiling.

Approximately 8 mL of blood will be taken at 1 h and 2 h post dosing. Approximately 10 mL, 20 mL, 40 mL, 60 mL, 80 mL and 40 mL will be taken at 4 h, 8 h, 12 h, 24 h, 48 h and 72 h hours, respectively, after drug administration ([Table 5.5.2: 3](#))

Table 5.5.2: 3 Blood volume to be taken for metabolic profiling

Time after dosing (h)	Blood volume (mL)
Pre-dose	8
1	8
2	8
4	10
8	20
12	40
24	60
48	80
72	40
Total	274

Proprietary confidential information © 2018 Boehringer Ingelheim International GmbH or one or more of its affiliated companies

For detailed description of blood sampling, sample handling, sample preparation, sample storage, tube labelling and sample shipment refer to the laboratory manual.

5.5.2.4

5.5.2.5 Urine sampling

During the trial urine will be collected at time points or in intervals as indicated in the [Flow Chart](#):

- to determine [¹⁴C]-radioactivity
- to determine concentrations of BI 730357

A blank sample will be taken within approximately 14 hours prior to drug administration.

For urine collection, addition of Tween 20 resulting in a final concentration of at least 0.05% Tween 20 is required. The weight of the containers has to be determined prior to (empty containers) and at the end of the collection interval. The urine volume (weight will be set equal to volume, i.e. 1 kg = 1 L, without correction for specific gravity of urine) for each collection interval will be documented. Volunteers will empty their bladders at the end of each sampling interval. The exact start and end times of the urine collection intervals will be recorded in the CRF.

All samples after intake of BI 730357 BS (C-14) are planned to be used for determination of [¹⁴C]-radioactivity.

Samples until and including the collection interval 312-336 h are planned to be used for analysis of BI 730357.

Samples to be used for metabolic profiling will be selected according to the levels of radioactivity in each urine sample.

For a detailed description of urine sampling, preparation of collection containers, sample storage, sample handling, labelling, and sample shipment refer to the laboratory manual.

5.5.2.6 Faeces sampling

Faeces will be collected for the analysis of [¹⁴C]-radioactivity and for metabolic profiling in intervals as indicated in the [Flow Chart](#). A blank sample will be taken within approximately 48 hours prior to drug administration. If several samples are available, the sample closest to drug administration will be used for analyses.

All faeces samples after intake of BI 730357 BS (C-14) are planned to be used for determination of [¹⁴C]-radioactivity.

Samples to be used for metabolic profiling will be selected according to the levels of radioactivity in each faeces sample interval.

All stools will be collected quantitatively in portions up to 336 hours after drug administration. The weight of the faeces and the exact times of faeces collection will be recorded in the eCRF.

If subjects are to collect faeces during the ambulatory phase of the study (see [Section 3.1](#) for release criteria), subjects are to collect faeces at home within 24 h intervals before admission to once-weekly in-house collection intervals. Home collection intervals are (if applicable): Days 20-21, 27-28, 34-35, 41-42, and 48-49. If faeces are collected in the subsequent in-house collection interval, faeces collected at home will be discarded. If no faeces is collected in the subsequent in-house collection interval (no defecation), faeces collected at home will be used instead for analysis

For a detailed description of faeces sampling, sample preparation, sample storage, labelling, and sample shipment refer to the laboratory manual.

5.5.2.7 Collection of vomit

If vomiting occurs in a volunteer within 12 h after drug administration, the vomit will be collected for determination of weight and [¹⁴C]-radioactivity.

For a detailed description of vomit sampling, sample preparation, sample storage, labelling, and sample shipment refer to the laboratory manual.

5.5.2.8 Further investigations

Back-up and left-over samples (plasma, urine, faeces; see laboratory manual for details) may be used for metabolic profiling if not needed for their primary purpose (bioanalysis and radiokinetic).

After completion of the trial, blood, plasma, urine, faeces samples (and vomit, if applicable) may be used for further methodological investigations, e.g. for stability testing of the drug and/or drug metabolites, assessment of drug metabolites. However, only data related to the analyte and/or its metabolite including anti-drug antibodies (if applicable) will be generated by these additional investigations.

The study samples will be discarded after completion of the additional investigations but not later than 5 years upon the final study report has been signed.

5.5.3 Analytical determinations

5.5.3.1 Analytical determinations of BI 730357 and plasma and BI 730357 urine concentrations

Plasma and urine concentrations of BI 730357 will be determined by a validated LC-MS/MS (liquid chromatography tandem mass spectrometry) assay. All details of the analytical method will be available prior to the start of sample analysis.

Analysis will be performed at:

Since this is an open label study, the bioanalyst will be unblinded during sample analysis.

5.5.3.2 Metabolic profiling

Determination of the metabolic pattern of BI 730357 in plasma, urine, and faeces including structure elucidation of the metabolites will be performed at

Metabolic profiling data will be reported separately from CTR.

5.5.3.3 Radiokinetic and Excretion Balance

Determination of [¹⁴C]-radioactivity concentrations in plasma, whole blood, urine, and faeces (and vomit, if applicable) will be done by means of validated liquid scintillation counting methods at

The blood, plasma, urine and faeces concentrations of radioactivity will be determined in agreement with relevant Standard Operating Procedures (SOPs).

6. INVESTIGATIONAL PLAN

6.1 VISIT SCHEDULE

Exact times of measurements outside the permitted time windows will be documented. The acceptable time windows for screening and end-of-trial examination are given in the [Flow Chart](#).

Study measurements and assessments scheduled to occur ‘before’ trial medication administration on Day 1 are to be performed and completed within a 3 h-period prior to the trial drug administration.

The acceptable deviation from the scheduled time for vital signs, ECG and laboratory tests will be \pm 30 min on Day 1 and \pm 90 min from Day 2 onwards in Visit 2.

If several activities, including ECG and meal intake, are scheduled at the same time point in the [Flow Chart](#), ECG should be the first and meal the last activity. Furthermore, if several measurements including venipuncture are scheduled for the same time, venipuncture should be the last of the measurements due to its inconvenience to the subject and possible influence on physiological parameters.

For planned individual plasma/blood concentration sampling times and urine/faeces sampling times or collection intervals refer to the [Flow Chart](#). While these nominal times should be adhered to as closely as possible, the actual sampling times will be recorded and used for determination of pharmacokinetic parameter. If beginning or end of a urine/faeces collection interval and a blood sample are scheduled for the same time point, urine/faeces collection should be done first, with withdrawal of the blood sample as close to the planned time point as possible.

If a subject misses an appointment, it will be rescheduled if possible. The relevance of measurements outside the permitted time windows will be assessed no later than at the Blinded Report Planning Meeting.

6.2 DETAILS OF TRIAL PROCEDURES AT SELECTED VISITS

6.2.1 Screening period

Screening visit is defined as Visit 1.

After having been informed about the trial, all subjects will give their written informed consent in accordance with GCP and local legislation prior to enrolment in the study.

For information regarding laboratory tests (including drug and virus screening), ECG, vital signs, and physical examination, refer to [Sections 5.2.3](#) to [5.2.5](#).

6.2.2 Treatment period

Each subject is expected to participate in one treatment period (Visit 2).

Proprietary confidential information © 2018 Boehringer Ingelheim International GmbH or one or more of its affiliated companies

On Day -1 of the treatment period study participants will be admitted to the trial site and kept under close medical surveillance until discharge from the trial site on Day 15. In the morning of Day 15, the subjects will then be allowed to leave the trial site after formal assessment and confirmation of their fitness.

Thereafter, until release criteria (see [Section 3.1](#)) have been reached, subjects will return to the trial site for up to 5 weekly 24-h collection intervals of urine and faeces. For these additional 24 h collection intervals, subjects will be admitted to the trial site on Days 21, 28, 35, 42, and 49. One day later, on Days 22, 29, 36, 43, and 50, respectively, subjects will be discharged from the trial site after formal assessment and confirmation of their fitness.

Within 24 h before each once-weekly in-house collection interval, subjects are to collect faeces at home (beginning of home collections on Days 20, 27, 34, 41, and 48). Faeces collected in these 24 h home-collection intervals will be used for analysis in case no defecation occurs in the subsequent 24 h in-house collection interval. E.g., if no defecation occurs in in-house collection interval Day 21-22, faeces of home-collection interval Day 20-21 will be used for analysis. If, however, faeces are collected in the subsequent 24 h in-house collection interval, faeces collected at home will be discarded. Once release criteria are reached, home collections will be stopped.

Irrespective of whether release criteria have been met or not after collection interval Days 49-50, no further collections are planned.

For details on time points and procedures for collection of blood/plasma/urine/faeces samples for PK analysis and mass balance assessment, refer to [Flow Chart](#) and [Section 5.5.2](#).

The safety measurements performed during the treatment period are specified in [Section 5.2](#) of this protocol and in the [Flow Chart](#). AEs and concomitant therapy will be assessed continuously from screening until the end-of-trial examination.

6.2.3 End-of-trial period

For AE assessment, laboratory tests, recording of ECG and vital signs, and physical examination during the end-of-trial period, see [Sections 5.2.2](#) to [5.2.5](#).

Subjects who discontinue treatment before the end of the planned treatment period should undergo the end-of-trial visit.

All abnormal values (including laboratory parameters) that are judged clinically relevant by the investigator will be monitored using the appropriate tests until a return to a medically acceptable level is achieved. (S)AEs persisting after subject's end of trial must be followed up until they have resolved, have been sufficiently characterised, or no further information can be obtained.

The end of the trial as a whole is defined by the 'last regular visit completed by last subject' or 'end date of the last open AE' or 'date of the last follow-up test' or 'date of an AE has been decided as sufficiently followed-up', whichever is latest.

7. STATISTICAL METHODS AND DETERMINATION OF SAMPLE SIZE

7.1 STATISTICAL DESIGN – MODEL

7.1.1 Objectives

The primary objective of this trial is to investigate the basic pharmacokinetics of BI 730357, [¹⁴C]-radioactivity, including mass balance, excretion pathways and metabolism following a single oral dose of 50 mg BI 730357 BS (C-14) given to healthy male subjects. The secondary objective of this trial is to determine PK parameters of [¹⁴C]-radioactivity, BI 730357 after single oral dose of BI 730357 BS (C-14) and to determine the routes and rates of elimination of BI 730357.

The assessment of safety and tolerability will be an additional objective of this trial, and will be evaluated by descriptive statistics. More details will be provided in the Trial Statistical Analysis Plan.

7.1.2 Endpoints

The basic pharmacokinetics of BI 730357 and [¹⁴C]-radioactivity, including mass balance, excretion pathways and metabolism is to be determined on the basis of the primary and secondary pharmacokinetic endpoints (see [Section 5.5.1](#)).

Additionally, the PK parameters listed in [Section 5.5.1.3](#) will be calculated and analysed descriptively, if feasible. Safety and tolerability will be determined on the basis of the parameters specified in [Section 5.2.1](#).

7.1.3 Model

No statistical model will be used.

7.2 NULL AND ALTERNATIVE HYPOTHESES

No confirmatory analysis will be conducted for this study. Data will be reported with descriptive statistics only.

7.3 PLANNED ANALYSES

Adherence to the protocol (such as inclusion/exclusion criteria, times of measurement, compliance with intake of trial medication, treatment dispensing errors, prohibited concomitant medication, completeness and consistency of data) will be checked. Important protocol deviations (iPDs) will be identified no later than in the Report Planning Meeting and provided in the TSAP.

Plasma/urine/faeces concentration data and parameters of a subject will be included in the statistical pharmacokinetic (PK) analyses if they are not flagged for exclusion due to a protocol deviation relevant to the evaluation of PK (to be decided no later than in the Report

Proprietary confidential information © 2018 Boehringer Ingelheim International GmbH or one or more of its affiliated companies

Planning Meeting) or due to PK non-evaluability (as revealed during data analysis, based on the criteria specified below). Exclusion of a subject's data will be documented in the CTR.

Relevant protocol deviations may be:

- Incorrect trial medication taken, i.e. the subject received at least one dose of trial medication the subject was not assigned to
- Incorrect dose of trial medication taken
- Use of restricted medications

Plasma, urine and faeces concentrations and/or parameters will be considered as non-evaluable, if for example

- a pre-dose concentration >5% of the C_{max} value of that subject
- missing samples/concentration data at important phases of PK disposition curve

The following subject and analysis sets will be defined for this trial:

Treated set (TS):

This subject set includes all subjects who were documented to have received one dose of study drug. This is the full analysis set population in the sense of ICH-E9.

PK analysis set (PKS):

The PK analysis set includes all subjects in the treated set who provide at least one value for primary or secondary PK endpoint and are not excluded according to the description above. Thus, a subject will be included in the PKS, even if he contributes only one PK endpoint value for the statistical assessment.

7.3.1 Primary analyses

The analysis of primary and secondary endpoints will be based on descriptive statistics only: number, arithmetic mean, standard deviation, minimum, median, maximum, arithmetic coefficient of variation, geometric mean, and geometric coefficient of variation. These evaluations will be based on the PKS. See [Sections 5.5.1](#) and [7.3.5](#) for further definitions of this analysis.

7.3.2 Secondary analyses

Refer to [Section 7.3.3](#) for a description of the analysis of safety.

7.3.3 Safety analyses

Safety will be assessed for the endpoints listed in [Section 5.2.1](#). All treated subjects (that is, all subjects who received at least one dose of study drug), will be included in the safety analysis. Safety analyses will be descriptive in nature and will be based on BI standards. No hypothesis testing is planned.

The analyses will be done by 'treatment at onset'.

Proprietary confidential information © 2018 Boehringer Ingelheim International GmbH or one or more of its affiliated companies

Tabulations of frequencies/proportions will be used for the evaluation of categorical (qualitative) data, and tabulations of descriptive statistics will be used to analyse continuous (quantitative) data.

Measurements (such as ECG, vital signs, or laboratory parameters) or AEs will be assigned to the treatment (see [Section 4.1](#)) based on the actual treatment at the planned time of the measurement or on the recorded time of AE onset (concept of treatment emergent AEs).

Therefore, measurements planned or AEs recorded prior to first intake of trial medication will be assigned to 'screening', those between first trial medication intake until end of the residual effect period (see [Section 1.2](#)) will be assigned to the treatment period. Events after the residual effect period but prior to end-of-trial examination will be summarized as 'follow-up'. These assignments including the corresponding time intervals will be defined in detail in the TSAP.

Adverse events will be coded using the Medical Dictionary for Regulatory Activities (MedDRA). Frequency, severity and causal relationship of AEs will be tabulated by treatment, system organ class and preferred term. SAEs, AESIs (see [Section 5.2.2.1](#)) and other significant AEs (according to ICH E3) will be listed separately.

Laboratory data will be compared to their reference ranges. Values outside the reference range as well as values defined as clinically relevant will be highlighted in the listings. Additionally, differences from baseline will be evaluated.

Vital signs or other safety-relevant data observed at screening, baseline, during the course of the trial and at the end-of-trial evaluation will be assessed with regard to possible changes compared to findings before start of treatment.

Relevant ECG findings as judged by the investigator will be reported as AEs.

7.3.4 Interim analyses

No interim analysis is planned.

7.3.5 Pharmacokinetic analyses

The pharmacokinetic parameters listed in [Section 5.5.1](#) will be calculated according to the BI SOP 'Standards and processes for analyses performed within Clinical Pharmacokinetics/Pharmacodynamics' [[001-MCS-36-472](#)].

Subjects who are not included in the PKS (refer to [Section 7.3](#)) will be reported with their individual plasma/urine/faeces concentrations and individual pharmacokinetic parameters; however, they will not be included in descriptive statistics for plasma/urine/faeces concentrations, pharmacokinetic parameters or other statistical assessment.

Only concentration values within the validated concentration range and actual sampling times will be used for the calculation of pharmacokinetic parameters. Concentrations used in the pharmacokinetic calculations will be in the same format provided in the bioanalytical report, (that is, to the same number of decimal places provided in the bioanalytical report).

The following descriptive statistics will be calculated for concentration-time data as well as for all pharmacokinetic parameters: number, arithmetic mean, standard deviation, minimum,

Proprietary confidential information © 2018 Boehringer Ingelheim International GmbH or one or more of its affiliated companies

median, maximum, arithmetic coefficient of variation, geometric mean, and geometric coefficient of variation. Descriptive statistics of pharmacokinetic parameters will be calculated using the individual values with the number of decimal places as provided by the evaluation program. Then the individual values as well as the descriptive statistics will be reported with three significant digits in the Clinical Trial Report.

If a pre-dose concentration value is greater than 5% of C_{max} , the subject's pharmacokinetic data will be not included in any statistical evaluations, in accordance with international guidances. The individual pharmacokinetic parameters of such a subject will be calculated and listed separately. If a pre-dose concentration is above BLQ, but less than or equal to 5% of the subject's C_{max} value, the subject's data without any adjustments will be included in all pharmacokinetic measurements and calculations.

7.4 HANDLING OF MISSING DATA

7.4.1 Safety

With respect to safety evaluations, it is not planned to impute missing values.

7.4.2 Blood/plasma/urine/faeces drug or [^{14}C]-radioactivity concentration - time profiles

Handling of missing PK data will be performed according to the relevant SOP of the Sponsor [\[001-MCS-36-472\]](#).

Drug concentration data identified with NOS (no sample available), NOR (no valid result), NOA (not analysed), BLQ (below the lower limit of quantification), or NOP (no peak detectable) will be displayed as such and not replaced by zero at any time point (this rule also applies also to the lag phase, including the pre-dose values).

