3. DESCRIPTION OF DESIGN AND TRIAL POPULATION

3.1 OVERALL TRIAL DESIGN AND PLAN

The study will be performed as a non-randomized, open-label, single-arm, single-dose trial in healthy male subjects in order to investigate the basic pharmacokinetics of BI 730357, and [¹⁴C]-radioactivity, including mass balance, excretion pathways and metabolism following a single oral dose of 50 mg BI 730357 BS (C-14).

A total of 6 healthy male subjects is planned to participate in the trial.

The planned radioactive dose per subject is 3.7 MBq (100.0 µCi, 0.14 mSv). This is equivalent to 0.038 mSv/MBq (please refer to [Appendix 10.1](#)).

On Day 1, subjects will receive the drug product, that is, 50 mg BI 730357 BS (C-14) and will then stay in the study centre up to the morning of Day 15 for collection of samples of blood, urine and faeces. Subjects will be readmitted to the study centre for 24 h collection intervals of urine and faeces on Days 21, 28, 35, 42, and 49, if release criteria have not been met before. Within 24 h before each of these once-weekly in-house collection intervals, subjects are to collect faeces at home. This 24-h interval home collection faeces will be used for analysis in case no defecation occurs in the subsequent 24 h in-house collection interval. Otherwise it will be discarded.

For determination of whether release criteria have been reached for individual subjects, [¹⁴C]-radioactivity will be measured in excreta (urine and faeces). The actual recovery results will be reported as a percentage of the administered dose.

If one of the following release criteria is true (i.e., release criteria have been met), 24 h collection intervals after Day 15 will not be performed / will be stopped:

- Greater than or equal to 90% of the administered dose has been recovered in urine and faeces combined over the investigational period

or

- If <1% of the dose administered has been collected in urine and faeces within 2 separate, consecutive 24-h intervals,

and

Concentration of total radioactivity in plasma and in blood is <5% of C_{max} of total radioactivity in plasma

If a subject is unable to attend one of these ambulatory visits, they may be allowed to reschedule the visit if needed. Irrespective of whether release criteria have been met or not after collection interval day 49-50, no further collections are planned.

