6.6 HANDLING OF MISSING DATA AND OUTLIERS

Data of screened subjects who were withdrawn from the trial prior to first administration of any study drug will not be reported in the CTR.

Data of subjects who failed to complete all periods of the study (dropouts or withdrawals) will be reported in the CTR as far as their data are available. All withdrawals will be documented and the reason for withdrawal recorded in the CTR.

CTP: *With respect to safety evaluations, it is not planned to impute missing values.*

The only exception where imputation might be necessary for safety evaluation are AE dates. Missing or incomplete AE dates are imputed according to BI standards (4) [001-MCG-156_RD-01].

Missing data and outliers of PK data are handled according to BI standards (5).

Blood/ Plasma/ Urine/ Faeces drug concentration or [¹⁴C]-radioactivity-time profiles

CTP: *Drug concentration data identified with NOS (no sample available), NOR (no valid result), NOA (not analysed), BLQ (below the lower limit of quantification), or NOP (no peak detectable) will be displayed as such and not replaced by zero at any time point (this rule also applies also to the lag phase, including the predose values).*

Pharmacokinetic parameters

CTP: *For the non-compartmental analysis, concentration data identified with NOS, NOR or NOA will generally not be considered. Concentration values in the lag phase identified as BLQ or NOP will be set to zero. All other BLQ/NOP values of the profile will be ignored. The lag phase is defined as the period between time zero and the first time point with a concentration above the quantification limit.*

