7. PLANNED ANALYSIS

The format of the listings and tables will follow the BI guideline "Reporting of clinical trials and project summaries" (6).

The individual values of all subjects will be listed, sorted by dose group, subject number and visit. AE listings will be sorted by assigned treatment (see [Section 7.8.1](#) below for details). The listings will be contained in Appendix 16.2 (SDL) of the CTR.

The following standard descriptive statistical parameters will be displayed in summary tables of continuous variables:

N	number of non-missing observations
Mean	arithmetic mean
SD	standard deviation
Min	minimum
Median	median
Max	maximum

For plasma concentrations as well as for all PK parameters, the following descriptive statistics will additionally be calculated:

CV	arithmetic coefficient of variation
gMean	geometric mean
gCV	geometric coefficient of variation

The data format for descriptive statistics of plasma concentrations will be identical with the data format of the respective concentrations. The descriptive statistics of PK parameters will be calculated using the individual values with the number of decimal places as provided by the evaluation program. Then the individual values as well as the descriptive statistics will be reported with three significant digits in the CTR.

Tabulations of frequencies for categorical data will include all possible categories and will display the number of observations in a category as well as the percentage (%) relative to the respective treatment. Percentages will be rounded to one decimal place. The category missing will be displayed if and only if there actually are missing values. Percentages will be based on all subjects in the respective subject set whether they have non-missing values or not.

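### Do below-LLOQ values and the blood-sampling stop make the late mean radioactivity profiles misleading enough to change the plan?

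*Protocol*

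**What the plan says.** Protocol section 7.3.5 plans n, mean, SD, minimum, median, maximum, CV, geometric mean and geometric CV at each time point: "The following descriptive statistics will be calculated for concentration-time data as well as for all pharmacokinetic parameters". Section 7.4.2 says that values coded as BLQ, not sampled, not analysed and so on "will be displayed as such and not replaced by zero at any time point". The sentence before it adds: "Handling of missing PK data will be performed according to the relevant SOP of the Sponsor". SAP section 6.6 repeats the display rule and says: "Missing data and outliers of PK data are handled according to BI standards". SAP section 7 defines N as the "number of non-missing observations" and also states: "The individual values of all subjects will be listed".

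On sampling, protocol section 5.5.2.2 provides that if plasma radioactivity is below 10 dpm/mL "at two consecutive time points for a subject, blood sampling can be stopped for this subject". Every sample up to and including 168 h must still be taken. The same section plans whole-blood and plasma radioactivity at every time point. Among the release criteria in section 3.1 is the condition "Concentration of total radioactivity in plasma and in blood is <5% of" the plasma maximum.

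**The concern.** Zero is ruled out as a substitute and no other value is named, so a programmer would probably average only the numeric results. Subjects whose radioactivity falls below the LLOQ would then drop out of the late means one by one. Those who remain have longer half-lives or higher exposure, which flattens the tail and makes radioactivity look more persistent relative to parent drug than it is.

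The stopping rule appears to make this worse, because a stopped subject has no later sample at all. It is also triggered by plasma alone although it ends whole-blood sampling too. If radioactivity stays longer in blood than in plasma, quantifiable blood values would be lost, and the blood part of the release criterion would receive no new data.

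**Working it through.** The plan gives no figure on this point to reproduce, so the check concerns the mechanism and its size.

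**LLOQ in mass units.** The dose is 3.7 MBq in 50 mg. 3.7 × 10⁶ Bq × 60 = 222,000,000 dpm; divided by 50 × 10⁶ ng this is 4.44 dpm/ng. So 10 dpm/mL = 10 / 4.44 = 2.25 ng-eq/mL.

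**Closed form if BLQ values are omitted.** Assume lognormal concentrations with s = √ln(1 + gCV²), z = ln(LLOQ / median) / s and P = 1 − Φ(z), the quantifiable fraction.

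- Inflation of the mean = Φ(s − z) / P
- Inflation of the geometric mean = exp(s·φ(z) / P)

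For gCV 40% (assumed), s = 0.385:

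| True median | BLQ | Mean | Geometric mean |
|---|---|---|---|
| equal to LLOQ | 50% | 0.650 / 0.5 = 1.30 | exp(0.385 × 0.798) = 1.36 |
| 0.8 × LLOQ | 72% | 0.423 / 0.281 = 1.51 | 1.59 |
| 0.6 × LLOQ | 91% | 0.173 / 0.092 = 1.88 | 1.99 |

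With gCV from 30% to 60% and 50% BLQ, the mean is inflated 1.23 to 1.42 times.

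**Six-subject simulation.** Settings: 20,000 replicates, mono-exponential decline, 10% assay noise, LLOQ 10 dpm/mL, and the stop applied after two consecutive BLQ results from 168 h. Half-lives of 28 h (parent) and 64 h (total radioactivity) come from the dosimetry report in protocol Appendix 10.1. V/F of 50, 150 or 500 L and a CV of 20% or 40% on starting level and half-life are assumptions. The table covers time points at which some but not all subjects were quantifiable.

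| Average number quantifiable, of 6 | Mean of quantifiable values / true mean |
|---|---|
| more than about 4.5 | about 1.2 to 1.4 |
| 2 to 4.5 | about 1.3 to 2.5 |
| fewer than 2 | about 1.8 to 5.5 |

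The stop removed a fraction of 0.0000 of the quantifiable plasma radioactivity values in every scenario, because a subject with two consecutive BLQ results on a declining curve would stay BLQ. The plasma bias therefore comes from omission alone.

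**Would a substitute value do better?** At the same time points, zero gave 0.55 to 1.00 times the true mean and makes a geometric mean impossible. LLOQ/2 gave 0.97 to 1.99 times, and 0.97 to 1.07 while two or more subjects were quantifiable. Each choice fails once few subjects remain.

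**Whole blood and the release criterion.** The blood condition is left unmet by the stop only if blood is at or above 5% of plasma Cmax while plasma is below 10 dpm/mL. That needs a blood-to-plasma ratio above 0.05 × Cmax / 10 = Cmax / 200. Taking Cmax as dose / (V/F), which is an upper figure:

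| V/F (assumed) | Cmax, dpm/mL | 5% of Cmax, dpm/mL | Ratio needed |
|---|---|---|---|
| 50 L | 4,440 | 222 | above 22 |
| 150 L | 1,480 | 74 | above 7.4 |
| 500 L | 444 | 22 | above 2.2 |

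A lower true Cmax reduces these thresholds in proportion. The documents give neither a blood-to-plasma ratio nor a blood LLOQ.

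**The case for a change.** The best case for a change is that omission is the natural reading. Zero is excluded, nothing else is offered, and a geometric mean needs positive numbers. The plan can state a BLQ rule when it wants to: protocol section 7.4.3 sets lag-phase values to zero and ignores the rest for the non-compartmental analysis. The SAP is meant to add technical detail, yet on this point it only repeats the protocol. A subject whose sampling was stopped would presumably be coded as having no sample, so n alone cannot separate BLQ from not drawn. Reporting a BLQ count and suppressing a mean that rests on few values would cost very little.

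The direction of the bias stands, and so does the remark that the SAP could have said more. The need for a change does not. The codes are shown in the listings, so BLQ and not sampled can be told apart for each of about six subjects. A falling n, and a minimum that never goes below the LLOQ, warn the reader of the table. A cut-off of two thirds quantifiable is a preference with no basis in the documents, and at gCV 40% it still allows the mean to be inflated 1.19 times. Counting undrawn samples as BLQ would mislabel exactly the whole-blood values that might have been quantifiable.

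The plasma-only trigger is a real asymmetry. Sampling may be stopped but need not be, and whole blood is also measured at the two time points that trigger the stop, so the investigator can see whether it is still high.

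**Conclusion.** The plan can stand as written. What is missing is a sentence on BLQ handling in descriptive concentration tables, which the sponsor's pharmacokinetic procedure is meant to supply and which analysts handle routinely. If BLQ values are omitted, the late means are too high: about 1.2 to 2.5 times while two or more of six subjects are quantifiable on average, and more beyond that. Those sizes rest on assumed V/F and between-subject CV. The published text contains no expected concentrations to show which scheduled times, if any, would be affected.

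Little depends on these profiles. The primary endpoints are recoveries in urine and faeces, which do not use plasma means. Cmax comes from each subject's own data, AUC0-tz stops at the last quantifiable point, and there is no model or hypothesis test. The possible loss of whole-blood values cannot be sized from the documents. For it to affect the release decision, blood would have to exceed plasma by a factor of Cmax / 200, with Cmax in dpm/mL.
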